7. STUDY OBJECTIVES AND PURPOSE

7.1. Primary Objective

The primary objective of this study is to evaluate the safety and tolerability of MDGN-002 administered by SQ injection to adults with moderate to severe, active CD or UC who have failed prior treatment with an anti-tumor necrosis factor alpha (anti-TNF α) agent.

7.2. Secondary Objectives

The secondary objectives of this study are to:

- Estimate plasma concentrations of MDGN-002 administered by SQ injection to adults with moderate to severe, active CD or UC.
- Evaluate response to treatment with MDGN-002 administered by SQ injection to adults with moderate to severe, active CD or UC.

8. INVESTIGATIONAL PLAN

8.1. Overall Study Design

This is a Phase 1b, multi-center, open-label, dose-escalation, signal-finding study to evaluate the safety, tolerability, PK and short-term efficacy of MDGN-002 in adults with moderate to severe, active CD or UC who have previously failed anti-TNF α treatment.

Four subjects with Crohn's disease who satisfy all eligibility criteria will be enrolled in each of 2 dose cohorts. The first cohort will receive MDGN-002 1.0 mg/kg SQ every 14 (q14) days. Dose escalation will proceed after all subjects in the first cohort have been enrolled and reached Visit 4 (Day 14 \pm 3 days), the safety data from those subjects has been reviewed by the Data Monitoring Committee, and a decision has been made to progress to the second cohort (see [Section 8.4](#)). The estimated dose escalation for the second cohort is 3.0 mg/kg SQ q14 days, if permitted by safety data review. After dose escalation has taken place 6 additional patients with UC will also be enrolled in the 3 mg/kg cohort.

Each subject's participation will include a screening period, which if required includes a wash-out period for subjects who have received biologic treatment within 12 weeks of the Screening Visit. With the exception of subjects requiring wash-out of the biologic certolizumab pegol (Cimzia), only those subjects without detectable biologic levels after 8 weeks of wash-out will be allowed to enter the study after confirmation of undetectable levels; all other subjects (including those receiving certolizumab pegol [Cimzia]) will be required to complete a full 12-week wash-out period. The wash-out period includes the time period from the last dose received prior to the Screening Visit. Subjects not requiring a biologic wash-out period will be allowed to enter the study after review and confirmation of eligibility at screening. Screening is followed by an 8-week, open-label treatment period, and a safety follow-up visit approximately 4 weeks after the last dose. The maximum study duration is 26 weeks.

Study visits will occur at screening and on Days 0, 7, 14, 21, 28, 35, 42, 49 and 56. The safety follow-up visit will occur on Day 84. The Schedule of Assessments is shown in [Table 1](#).

Table 1 Schedule of Assessments

Assessment or Procedure	Screening Period				Open-Label Treatment Period										Safety Follow-up	
	Visit 1	Initial Phone Contact ^a	Visit for Testing Previous Biologics (if required)	Wash-out Phone Contact ^b	Visit 2 ^c		Visit 3 Day 7	Visit 4 Day 14	Visit 5 Day 21	Visit 6 Day 28	Visit 7 Day 35	Visit 8 Day 42	Visit 9 Day 49	Visit 10 / ET Visit Day 56		
					Pre-dose Day 0	Dosing and Post-dose Day 0										
Informed consent	X															
Inclusion/exclusion criteria review	X	X			X											
Testing for Previous Biologics			X ^d													
Genotyping for DcR3 genes (CD only)	X															
Demographics / medical history ^d	X															
Physical examination, incl. weight ^e	X				X			X		X		X		X		
Vital signs (BP, pulse, RR, T) ^f	X				X	X		X		X		X		X		
TB testing ^g	X															
12-lead ECG	X									X				X		
Clinical laboratory assessments ^h	X				X			X		X		X		X		

Assessment or Procedure	Screening Period				Open-Label Treatment Period										Safety Follow-up	
	Visit 1	Initial Phone Contact ^a	Visit for Testing Previous Biologics (if required)	Wash-out Phone Contact ^b	Visit 2 ^c		Visit 3 Day 7	Visit 4 Day 14	Visit 5 Day 21	Visit 6 Day 28	Visit 7 Day 35	Visit 8 Day 42	Visit 9 Day 49	Visit 10 / ET Visit Day 56		
					Pre-dose Day 0	Dosing and Post-dose Day 0										
Adverse event monitoring ^o	X	X	X	X	X	X	X	X	X	X	X	X	X	X	X	
Concomitant medications	X	X	X	X	X	X	X	X	X	X	X	X	X	X	X	
Provide/re- confirm access to subject diary	X				X		X	X	X	X	X	X	X	X		
Subject diary reviewed for completeness					X		X	X	X	X	X	X	X	X		
Assess individual subject stopping criteria						X	X	X	X	X	X	X	X	X		
MDGN-002 administration (on-site) ^p						X		X		X		X				

^a Telephone visit is conducted for confirmation of eligibility. If the subject is not currently receiving biologic treatment, they will begin completing the subject diary and have visit 2 scheduled >7 days from the diary being initiated. The diary should be completed up to the time of the visit.

^b Telephone visit is conducted for confirmation whether additional wash-out time is required following receipt and review of the laboratory results. If the concentration level is not detectable, the subject will have their visit scheduled >7 days from the time the subject started completing the diary. If the concentration level is detectable, the subject will complete the full 12 week wash-out. The diary should be completed up to the time of the visit.

^c After Day 0 (Visit 2), visits at which MDGN-002 is administered should occur every 14 ± 3 days. These visits should be scheduled relative to Day 0 (Visit 2), which is the baseline visit.

^d Medical history will include details regarding all UC/CD-related surgical procedures and hospitalizations.

^e A complete physical examination will be performed at Visits 1, 2, 6, and 10/ET. Brief physical examinations will be done at Visits 4 and 8. Height will be measured at V2 only.

^f Vitals will be taken pre-and post-dose on Visit 2, 4, 6 and 8. Post-dose vitals should be taken at least 60 minutes post-dose, immediately prior to discharge.

^g TB testing will include QuantiFERON-TB Gold (QFT) blood testing or PPD skin testing. If the subject's PPD tine skin test is ≥ 5 mm, a chest x-ray will also be employed for TB assessment.

^h Clinical laboratory assessments at Visits 1, 6, and 10/ET include: CBC with differential, hematology, serum albumin, CRP, liver panel, GGT. Anti-drug antibodies will be measured at Visits 2, 6 and 10. Clinical laboratory assessments at Visits 2, 4, and, 8 include hematology and serum albumin.

ⁱ Pre-dose PK blood samples will be obtained within 60 minutes prior to dose at Visits 2, 4, 6 and 8.

^j Exploratory analyses will examine LIGHT, cytokines, RNA sequencing, and flow cytometry.

^k Serum β -hCG will be conducted at Visit 1 and Urine β -hCG tests will be conducted on Visits 2, 6 and 10.

^l Screening for amphetamines, barbiturates, benzodiazepines, cocaine, opiates, phencyclidine, cannabinoids, propoxyphene, and methadone as warranted.

^m Stool samples will be obtained at Visits 1, 6 and 10/ET. C.difficile test will be performed only at Visit 1. Fecal calprotectin will be measured at all specified visits.

ⁿ Histological confirmation of disease is performed only at Visit 1. Documentation will be provided to site for confirmation or prior documentation of histological confirmation is acceptable. Exploratory biomarker histology will be completed for samples provided to study central laboratory provider.

^o Adverse event monitoring begins at the time informed consent is signed.

^p Subjects will be required to remain in the clinic for at least 60 minutes after MDGN-002 administration for adverse event monitoring.

^q Subjects requiring wash-out will have a blood test performed at 8 weeks after the start of the wash-out period to confirm the previous biologic therapy is undetectable. If there is no previous biologic therapy detected, subjects will be able to continue onto Visit 2 and will not be required to complete the full 12-week wash-out. If there are detectable levels of the previous biologic therapy, then subjects will complete the full 12-week wash-out before proceeding to Visit 2. For subjects receiving certolizumab pegol (Cimzia) a 12-week wash-out is required.

^r The Modified Mayo Score includes stool frequency, rectal bleeding, and the appearance of mucosa upon endoscopy. This score will be calculated at Visit 1 and Visit 10 using the endoscopy score from the central reader, self reported data on stool frequency and rectal bleeding from the period prior to the subject being screened for Visit 1 and data from the patient diary for Visit 10.

BP=blood pressure; CBC=complete blood count; CDAI=Crohn's Disease Activity Index; CRP=C-reactive protein; DcR3=decoy receptor 3; GGT=gamma-glutamyl transferase; ECG=electrocardiogram; ET=early termination; hCG=human chorionic gonadotropin; LIGHT=Lymphotoxin-like, exhibits Inducible expression, and competes with Herpes Virus Glycoprotein D for Herpesvirus Entry Mediator, a receptor expressed by T lymphocytes; PK=pharmacokinetic; PPD = purified protein derivative; RR=respiration rate; T=temperature; TB=tuberculosis; TNF α =tumor necrosis factor alpha.

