8.2.2. Open-label Treatment Period

Eligible subjects will return to the clinic after the screening period (and wash-out period, if applicable) on Visit 2, which is Day 0 of the 8-week, open-label treatment period. Physical examinations including weight and vital sign assessments, clinical laboratory tests, urinalysis, and the CDAI (CD only) will be performed. A urine β -hCG test will be administered to females of childbearing potential. Any AEs and concomitant medications will be recorded. Blood will be drawn for PK, ADA and exploratory analyses (including LIGHT, cytokines, RNA sequencing, and flow cytometry). Subjects with CD will record their daily assessment of well-being, abdominal pain and stool frequency including loose and watery stools daily in their study diary. Subjects with UC will record stool frequency and rectal bleeding daily in their study diary. Diary data will be reviewed for completeness during each visit. Subjects will be re-evaluated to determine whether they meet all inclusion criteria and do not satisfy any of the exclusion criteria.

Eligible subjects will then be enrolled in the study and receive their first dose of MDGN-002 in the clinic. Subjects will receive MDGN-002 as a SQ injection in the abdomen in a zone of 4 to 10 cm from the umbilicus with the injection site rotated with each subsequent dose. The dose of MDGN-002 will be administered every 14 days (\pm 3 days) for 8 weeks. Subjects will be monitored for AEs during the administration of each dose and for 60 minutes after dosing.

Subjects will return to the clinic every 14 (\pm 3) days (Visits 4, 6, 8, and 10) after the first MDGN-002 dose for assessment of safety, PK, and efficacy and to receive the next dose of investigational product, as shown in [Table 1](#). Additional weekly visits between dosing visits (Visits 3, 5, 7, and 9) will occur at which time blood will be drawn for PK analyses, subjects will be provided access to a study diary for diary data collection, and AEs and concomitant medication use will be recorded.

Prior to enrolling subjects in the second dose cohort, all subjects in the first cohort will have reached Visit 4 (Day 14 \pm 3 days) in the study and safety data from those subjects will be reviewed by the Data Monitoring Committee (DMC; as described in [Section 8.4](#)). A recommendation will be provided by the DMC and a decision by the Sponsor whether subjects can be enrolled in the next dose cohort.

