8.4. Data Monitoring Committee

An external, independent Data Monitoring Committee (DMC) comprising physicians, scientists and a biostatistician will review the study data at a meeting after all subjects in the first cohort have been enrolled and reached Visit 4 (Day 14 ± 3 days), and after completion of the second cohort. Additionally, ad hoc meetings to assess individual exacerbations of CD or UC meeting Common Terminology Criteria for Adverse Events (CTCAE) Grade 3 or greater as defined in [Section 8.5](#) may be held. The DMC's role is to protect the interests of the subjects in the study and those still to be entered in the study by reviewing information such as safety, tolerability, pharmacokinetic and efficacy data. The DMC's meeting schedule may be adjusted based on recommendations made by the DMC, the amount of incremental safety data, and other practical considerations. The data provided to the DMC may not be monitored and will not be considered "clean" until the database is locked at the completion of the study.

Possible outcomes of the DMC review can include one of the following recommendations:

- Study can continue
- Study can continue with modifications
- Study is to be terminated

Data Monitoring Committee recommendation will be documented in meeting minutes which will include, at a minimum:

- List of meeting participants
- Summary of data considered during the meeting
- Summary of the DMC recommendation regarding further dose cohorts, including any concerns raised

The sponsor is responsible for the decision to continue, modify or terminate the study. A copy of the DMC meeting recommendation and sponsor decision will be sent to the study sites upon completion and prior to administration of the next subject dose in the second cohort.

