8.5. Individual Subject and Study Stopping Criteria

8.5.1. Individual Subject Stopping Criteria

The following individual subject stopping criteria will be used during the study and will be assessed starting post-dose at Visit 2:

- A subject develops a CTCAE Grade 3 or higher of the following:
 - Injection site reactions
 - Opportunistic infections (i.e. tuberculosis)
 - Hypersensitivity reactions (e.g. allergic reactions, anaphylaxis or cytokine release syndrome)
 - Malignancy
 - Decreased white blood cell count
 - Decrease neutrophil count
 - Decreased platelets
 - Colonic or ileal hemorrhage
 - Colonic, ileal or small intestine obstruction
 - Colonic, ileal or small intestine perforation
 - Colonic, ileal or small intestine stenosis
- A subject will also be stopped if liver enzymes are:
 - ALT or AST >8x ULN
 - ALT or AST >5x ULN for more than 2 consecutive weeks or
 - A single subject ALT or AST >3x ULN with the appearance of fatigue, nausea, vomiting, right upper quadrant pain or tenderness, fever, rash and or eosinophilia (>5%).

Note: subjects who exhibit ALT or AST >3x ULN without appearance of any of the above symptoms must have repeat testing within 48-72 hours to confirm abnormality and determine direction (increase or decrease) from the original value.

- A subject will be stopped if Hy's Law is detected (i.e. ALT or AST >3x ULN and total bilirubin >2x ULN and no other reason can be found to explain the combination of increased AT and TBL, such as viral hepatitis A, B, or C; preexisting or acute liver disease; or another drug capable of causing the observed injury).

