8.5.2. Study Stopping Criteria

The following study stopping criteria will be used during the study:

- The study will be stopped if two or more subjects develop the same CTCAE Grade 3 or if one subject develops a CTCAE Grade 4 of the following:
 - Injection site reactions
 - Opportunistic infections (i.e. tuberculosis)
 - Hypersensitivity reactions (e.g. allergic reactions, anaphylaxis or cytokine release syndrome)
 - Malignancy

- Decreased white blood cell count
 - Decrease neutrophil count
 - Decreased platelets
- The study will be stopped if two individual subjects develop any of the following liver toxicities:
 - ALT or AST >8x ULN
 - ALT or AST >5x ULN for more than consecutive 2 weeks or
 - ALT or AST >3x ULN with the appearance of fatigue, nausea, vomiting, right upper quadrant pain or tenderness, fever, rash and or eosinophilia (>5%).
- The study will be stopped if one subject meeting Hy's Law is detected (i.e. ALT or AST >3x ULN and total bilirubin >2x ULN and no other reason can be found to explain the combination of increased AT and TBL, such as viral hepatitis A, B, or C; preexisting or acute liver disease; or another drug capable of causing the observed injury).
- Individual reports of exacerbations of Crohn's disease CTCAE Grade 3 or greater, such as:
 - Colonic or ileal hemorrhage
 - Colonic, ileal or small intestine obstruction
 - Colonic, ileal or small intestine perforation
 - Colonic, ileal or small intestine stenosis

will be reviewed by the DMC at the first available date after report to determine if modifying the study or stopping the study is recommended.

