8.8. Treatment Assignment

The first cohort of subjects will be assigned to the 1.0 mg/kg dose of MDGN-002. Subjects will be assigned to the second dose cohort, after the DMC review of the safety data from the first cohort, as described in [Section 8.4](#), provided study stopping criteria have not been met as described in [Section 8.5.2](#) and a decision is made by the Sponsor that enrolment can continue.

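### The liver stopping rules are a condition of escalating to 3 mg/kg, but no text requires ALT, AST or bilirubin at Visit 4, the visit that triggers the DMC review

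*Protocol*

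**What the plan says.** **The gate.** Section 8.1 states: "Dose escalation will proceed after all subjects in the first cohort have been enrolled and reached Visit 4", and goes on to require DMC review of those subjects' safety data and a decision to progress. Section 8.2.2 repeats the timing ("all subjects in the first cohort will have reached Visit 4"), as does Section 8.4 for the DMC meeting ("after all subjects in the first cohort have been enrolled and reached Visit 4"). Section 8.8 allows assignment to the second cohort "provided study stopping criteria have not been met as described in" Section 8.5.2, subject to a sponsor decision. Section 6.3 adds that escalation depends on the absence of important safety findings in cohort 1.

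**The liver criteria.** Section 8.5.2 reads: "The study will be stopped if two individual subjects develop any of the following liver toxicities". It then lists three ALT/AST rules: above 8 times ULN; above 5 times ULN lasting more than two weeks; above 3 times ULN with symptoms. A single Hy's Law case also stops the study. Under Section 8.5.1, subjects above 3 times ULN without symptoms "must have repeat testing within 48-72 hours to confirm abnormality and determine direction".

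**The laboratory schedule.** Section 12.1.5 (Visit 4) asks for a clinical laboratory sample without naming analytes. Section 12.3.1.5.1 lists ALT, AST and total bilirubin under serum chemistry but leaves timing to Table 1. Footnote h of that table gives two lists:
- "Clinical laboratory assessments at Visits 1, 6, and 10/ET include: CBC with differential, hematology, serum albumin, CRP, liver panel, GGT"
- "Clinical laboratory assessments at Visits 2, 4, and, 8 include hematology and serum albumin"

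**What the DMC receives.** Section 8.4 describes the data in general categories and sets no minimum content or cut-off. SAP Section 13 leaves further detail to a DMC charter, which is not among the documents.

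**The concern.** The protocol makes the liver criteria a condition of a threefold dose increase. The ALT/AST rules cannot be judged without transaminases, and Hy's Law also needs total bilirubin. If a site and its laboratory follow footnote h to the letter, the DMC meets at a point where some cohort 1 subjects have no post-dose value for any of these. The criteria would then be unmet because nothing was measured.

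Other safeguards do not close this gap. The repeat-test rule in Section 8.5.1 starts only after a raised value has been found. Table 1 marks the individual stopping criteria for assessment at Visit 4, but names no liver test there to inform that assessment. Weekly investigator review (Section 8.3), adverse event questions and unscheduled samples can pick up a symptomatic case, but they do not ensure that a symptom-free rise is measured. Safety is the primary objective and cohort 1 has four subjects, so each unmeasured subject is a quarter of the evidence for the decision.

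**Working it through.** **Inputs.** Visit 4 is Day 14 ±3 (Section 12.1.5) and Visit 6 is Day 28 ±3 (Section 12.1.5.2). Laboratory visits are 1, 2, 4, 6, 8 and 10 (Table 1). Liver panels are named at 1, 6 and 10/ET (footnote h). Screening lasts about 2 weeks (Section 12.2) and up to 14 weeks (Section 12.1.1). Sample volumes and counts come from Table 3.

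**1. The plan's own figure.** Table 3, volume × number, in mL:
12.0 + 21.0 + 4.0 + 18.0 + 10.0 + 9.0 + 7.5 + 10.5 + 6.0 + 6.0 = 104.0. The stated total is reproduced. The chemistry row is 3.5 × 6 = 21.0, and its six samples equal the number of laboratory visits. A chemistry tube therefore appears to be drawn at Visits 2 and 4, although the table does not say what is run on it.

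**2. Named liver panels after the first dose and up to Visit 4.** Of Visits 1, 6 and 10/ET, none falls in this interval, so the count is 0.

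**3. Gap from trigger to first named on-treatment panel.**
- Nominal: 28 − 14 = 14 days
- Shortest: 25 − 17 = 8 days
- Longest: 31 − 11 = 20 days

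**4. Who is affected.** At the earliest trigger, the last cohort 1 subject still on treatment has only just reached Visit 4 and so has no named post-dose panel. Another subject has one only if dosed earlier than the last by at least the gap in step 3, or if terminated early (Section 12.1.6 asks for the Visit 10 procedures then). The enrolment pace is not given, so the number affected is at least that last subject and may be more.

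**5. Age of the last subject's most recent named panel at nominal Visit 4.** This is the screening panel.
- Screening of 2 weeks: 14 + 14 = 28 days
- Screening of 14 weeks: 98 + 14 = 112 days (98 + 17 = 115 at the late edge of the window)
- 28 days is not a floor. Section 12.1.2 allows Visit 2 from Day 8 of the diary; if the diary starts on the day of the screening panel, the age is about 8 + 14 = 22 days.

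**6. What a Visit 4 panel can settle.** It informs the rules for above 8 times ULN, above 3 times ULN with symptoms, and Hy's Law. It cannot by itself settle the two-week rule. A first value above 5 times ULN on Day 14 has lasted more than 14 days only from Day 29, one day after nominal Visit 6.

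**The case against.** The strongest reply is that footnote h is shorthand. It says that the assessments include certain tests, and it is visibly incomplete. It omits the Visit 4 ADA sample that Section 12.1.5 collects. It names neither creatinine nor eGFR at any visit, although a low eGFR is exclusionary in Section 9.2. Against the literal reading stand the chemistry list in Section 12.3.1.5.1, the six chemistry samples in Table 3, and the by-visit laboratory summaries in Protocol Section 13.1.2 and SAP Section 9.3.

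This stands as evidence that full chemistry may be intended at Visit 4, but it does not amount to a requirement. Albumin is itself on the serum chemistry list, so a chemistry tube and a by-visit chemistry table are both consistent with albumin alone. If both parts of footnote h meant the full panel, there would be no purpose in naming the liver panel and GGT in one and not in the other.

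Second, escalation is not automatic. A reader might infer from the timing sentence that reaching Visit 4 is enough. It is not: DMC review and a sponsor decision are also required. Laboratory tests count as safety assessments (Section 12.3.1), and Section 8.4 lets the meeting schedule be adjusted. Any liver results that exist should therefore reach the DMC, and the charter may say so. But review cannot supply a value that was never measured, and Sections 8.1, 8.2.2 and 8.4 do not make the decision wait for pending results.

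Third, the gate may already have passed. The synopsis estimates first enrolment in 2Q2017, and the SAP cites protocol version 11.0 of July 2021. The documents do not confirm this, and the current text is still prospective. If it has passed, naming the analytes still serves the liver stopping rules for the remaining 3 mg/kg subjects, including those with UC.

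**Conclusion.** The gap is one of requirement. The protocol ties escalation to liver criteria without requiring the measurements that inform them by the time of the decision. On a literal reading of footnote h, at least the last cohort 1 subject still on treatment has no scheduled post-dose ALT, AST or bilirubin at the earliest trigger, and the first named panel follows 14 days later (8 to 20). This assumes that the decision falls at that earliest point. If full chemistry is in fact run at Visit 4, what remains is unclear wording and the absence of a rule to wait for results.

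Three stronger readings are not supported:
- That liver tests will not be done at Visit 4, or that all four cohort 1 subjects will lack them. The text leaves both open.
- That liver risk is high. The non-clinical and earlier clinical data are not visible, so nothing can be said about it. The point rests only on the protocol's own condition for escalation.
- That one subject above 5 times ULN must by rule halt escalation. The study-level ALT/AST rules need two subjects, so such a hold would be a new and stricter criterion.

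Confidence is moderate, because the intended Visit 4 panel is uncertain and the charter is not available.

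**What to change.** 1. In Table 1 footnote h, name ALT, AST and total bilirubin at Visit 4, and at Visit 2 as a current pre-dose baseline. Run them on the chemistry samples that Table 3 already counts.
2. In Sections 8.1, 8.2.2 and 8.4, require that each cohort 1 subject's Visit 4 (or early termination) liver results, and any 48-72 hour repeat triggered under Section 8.5.1, be available to the DMC before the escalation decision.

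A value above 5 times ULN whose duration is not yet known should be left to the DMC, which can already recommend continuing with modifications.

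**Cost.** Three analytes at two visits. No additional scheduled blood is needed if the counted chemistry tubes are used, so the Table 3 total stays 104.0 mL. The DMC waits a short time for the last subject's results. Repeat samples arise only for a raised value, and Section 8.5.1 already requires them for symptom-free rises above 3 times ULN. If full chemistry at Visit 4 was always intended, item 1 is only a clarification and the wait in item 2 is the sole change in practice.
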